#### 6.1.2. Previous Ulcerative Colitis Treatment

Previous ulcerative colitis treatment will be analyzed as treatment which purpose is to treatment UC and checking 'Yes' for "terminated prior to administration of Xeljanz®", on 'concomitant medication' page of eCRF.

## **Statistical Analysis Plan for rPMS**

- 1) Previous ulcerative colitis treatment will be presented in frequency and percentage.
- 2) Previous ulcerative colitis treatment classified by Level 1 and Level 2 according to the latest version of Anatomical Therapeutic Chemical (ATC) classification system in detail will be summarized with the number of subjects having concomitant medication, percentage and the number of concomitant medication.

### 6.1.3. Medical History

- 1) Other past/present diseases will be presented in frequency and percentage.
- 2) Other past/present diseases classified by System Organ Class (SOC) and Preferred Term (PT) according to the latest version of Medical Dictionary for Regulatory Activities (MedDRA) will be summarized with the number of subjects having other past diseases, percentage and the number of other past diseases.
- 3) Renal impairment will be presented in frequency and percentage.
- 4) Hepatic impairment will be presented in frequency and percentage.

### 6.1.4. Concomitant Medication

Concomitant medication will be analyzed as all treatment included present ulcerative colitis treatment and other concomitant medication except previous ulcerative colitis treatment.

- 1) Concomitant medication will be presented in frequency and percentage.
- 2) Concomitant medication classified by Level 1 and Level 2 according to the latest version of ATC classification system in detail will be summarized with the number of subjects having concomitant medication, percentage and the number of concomitant medication.

### 6.1.5. Administration Status of Xeljanz®

- 1) Total duration of administration (day) will be presented in n, mean, SD, median, minimum and maximum. Also, frequency and percentage of each group categorized according to the distribution for total duration of administration will be presented.

$$\text{Total duration of administration (day)} = \sum_{\text{First}}^{\text{Last}} (\text{End treatment} - \text{Start treatment} + 1)$$

- 2) Total dose of administration (mg) will be presented in n, mean, SD, median, minimum and maximum.

Total dose of administration (mg)

$$= \sum_{\text{First}}^{\text{Last}} \{ \text{Dose per administration} \times \text{Daily dosing frequency} \\ \times (\text{End treatment} - \text{Start treatment} + 1) \}$$

- 3) Daily average dose of administration (mg/day) will be presented in n, mean, SD, median,

## **Statistical Analysis Plan for rPMS**

minimum and maximum. Also, frequency and percentage of each group categorized according to the distribution for daily average dose of administration will be presented.

$$\text{Daily average dose of administration (mg/day)} = \frac{\text{Total dose of administration (mg)}}{\text{Total duration of administration (day)}}$$

### 6.1.6. Completion of the treatment and reasons of discontinuation

Completion of the 24 weeks treatment (52 week of treatment for long-term user) will be presented in frequency and percentage. For the subjects who have not completed the 24 weeks of treatment (52 week of treatment for long-term user), the reasons of discontinuation will be presented in frequency and percentage.

## 6.2. Safety Analyses

Safety analyses will be performed based on data of safety analysis set. All adverse events in CRF will be classified by SOC and PT according to the latest version of MedDRA.

- 1) All adverse events investigated after administration of Xeljanz® during the study will be summarized with the number of subjects having adverse events, incidence of adverse events with 95% confidence interval (C.I) and the number of adverse events by categorizing as follows:
  - Serious adverse events and serious adverse drug reactions
  - Unexpected serious adverse events and unexpected serious adverse drug reactions
  - Unexpected adverse events and unexpected adverse drug reactions
  - Adverse events and adverse drug reactions
  - Adverse events of safety concerns\*

\*Adverse event with important identified risks and important potential risks in relation to the safety specification under the risk management plan

- 2) All adverse events investigated after administration of Xeljanz® during the study will be summarized with the frequency and percentage of adverse events by categorizing as follows:
  - Occurrence status of adverse events by their severity
    - Mild
    - Moderate
    - Severe
  - Occurrence status of adverse events by their outcome
    - Recovered
    - Recovered with sequelae
    - Recovering
    - Not recovered
    - Unknown

## **Statistical Analysis Plan for rPMS**

- Occurrence status of adverse events by their seriousness [SAE]
  - Results in death
  - Is life-threatening
  - Requires inpatient hospitalization or prolongation of hospitalization
  - Results in persistent or significant disability/incapacity
  - Results in congenital anomaly/birth defect
  - Other important medical event
- [Non-SAE]
- Occurrence status of adverse events by action taken
  - Permanently discontinued
  - Temporary discontinued or delayed
  - Dose reduced
  - Dose increased
  - No change
  - Not applicable
- Occurrence status of adverse events by their causality assessment to Xeljanz®
  - Related to Xeljanz®: ① Certain  
② Probable/likely  
③ Possible  
⑤ Conditional/unclassified  
⑥ Unassessable/unclassifiable  
⑦ Not applicable
  - Not related to Xeljanz®: ④ Unlikely
- Occurrence status of adverse events by their other causality assessment (In case of 'Unlikely')
  - Disease under the study
  - Other diseases
  - Concomitant treatment-medication or non-medication
  - Other

3) Occurrence status of adverse events by demographic and other baseline characteristics

- The incidence of adverse events and 95% C.I will be presented by categorical variables of demographic and other baseline characteristics.
- To identify statistically significant difference in the incidence of adverse events by categorical variables of demographic and other baseline characteristics, Chi-square test ( $\chi^2$  test) or Fisher's exact test (if the expected frequency for each cell under 5 is more than 20%) will be performed.

## **Statistical Analysis Plan for rPMS**

- 4) Analysis of factors that affect the safety
  - In the re-examination report, logistic regression of multivariate analysis will be performed and an odds ratio with 95% C.I and p-value will be presented to identify the factors that affect incidence of adverse events in demographic and other baseline characteristics.
- 5) Analysis for special patient populations [geriatric subjects (aged  $\geq$  65 years), subjects with renal impairment, subjects with hepatic impairment]
  - Adverse events and adverse drug reactions collected in each special patient population will be presented the number of subjects having adverse events, incidence of adverse events and the number of adverse events for each SOC and PT.
- 6) Analysis for population excluded from safety analysis
  - All adverse events investigated after administration of Xeljanz® for population excluded from safety analysis will be summarized with the number of subjects having adverse events, incidence of adverse events with 95% C.I and the number of adverse events by categorizing as follows.
    - Serious adverse events and serious adverse drug reactions (in the re-examination report only)
    - Unexpected serious adverse events and unexpected serious adverse drug reactions (in the re-examination report only)
    - Unexpected adverse events and unexpected adverse drug reactions (in the re-examination report only)
    - Adverse events and adverse drug reactions

### 6.3. Efficacy Analyses

Efficacy analyses will be performed based on data of efficacy analysis set

- 1) Mayo index, Mayo score and partial Mayo score
  - Mayo index (stool frequency, rectal bleeding, physician's global assessment and finding of endoscopy), Mayo score or partial Mayo score at baseline, week 8 ( $\pm 15$  days), week 16 ( $\pm 15$  days), week 24 ( $\pm 15$  days) and changes from the baseline to last value will be presented in n, mean, SD, median, minimum and maximum. And changes from the baseline to last values will be tested by using paired t-test (or Wilcoxon signed rank test).
- 2) Mucosal healing (If endoscopy was done)
  - Mucosal healing at week 8 ( $\pm 15$  days), week 16 ( $\pm 15$  days), week 24 ( $\pm 15$  days) will be presented in frequency and percentage.
    - Achieved
    - Not achieved
- 3) Remission
  - Remission at week 8 ( $\pm 15$  days), week 16 ( $\pm 15$  days), week 24 ( $\pm 15$  days) will be

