7.2.5. Study procedures

Patients will be enrolled by continuous registration method. The investigator should enroll all patients to whom Xeljanz is prescribed for the first time according to the local product label and who agree to participate in this study by signing the data privacy statement (used in place of the informed consent form). Xeljanz will be medicated by the investigator's prescription under usual clinical practice. Pfizer Korea will not provide the medicinal product for this study.

There will be no mandatory visit during the study. The investigators will collect relevant data from the time of initiating administration of Xeljanz until 24 weeks of treatment (52 weeks of treatment for the long-term users). If the patient does not complete 24 or 52 weeks of treatment, relevant data should be collected based on the last assessment performed at the time of treatment discontinuation. The investigator should record the following information on the patient's CRF.

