7.7.2. Effectiveness analysis

Effectiveness analysis will be performed for all patients entering this study for the safety analysis whose effectiveness data are available after 24 weeks of treatment, or based on the last assessment performed at the time of treatment discontinuation if the patient does not complete the 24 weeks of treatment. If the patient does not complete the 24 weeks of treatment, the cause of discontinuation will be assessed. For the long-term users, effectiveness analysis will also be performed after the 52 week of the treatment. Cause of discontinuation will also be performed for the long term users if the patient does not complete the 52 weeks of treatment.

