### 3.2. Efficacy Analysis Set

The Efficacy analysis set will be included all patients entering this study for the safety analysis whose efficacy data are available after 24 weeks of treatment, or based on the last assessment performed at the time of treatment discontinuation if the patient does not complete the 24 weeks of treatment. If the patient does not complete the 24 weeks of treatment, the cause of discontinuation will be assessed.

The cases below shall be excluded from the efficacy analysis set in the following order:

- 1) Subjects who are excluded from the safety analysis set
- 2) Subjects without general efficacy assessment by the investigator
- 3) Subjects who are evaluated general efficacy assessment as 'Not assessable' by the investigator
- 4) Subjects who are have been administrated Xeljanz® for less than 8 weeks (56 days)

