### 4.2. Efficacy Endpoints

The Mayo score or the partial Mayo score at week 8, 16, 24 and also 52 for the long-term users is assessed to see the remission, clinical response or mucosal healing. Investigator will perform the final efficacy evaluation of the drug into 4 categories based on the clinical impression plus Mayo score or partial Mayo score ('Improved', 'Unchanged', 'Aggravated', 'Not assessable').

If the patient does not complete the 24 or 52 weeks of treatment, relevant data should be collected based on the last assessment performed at the time of treatment discontinuation. The final efficacy evaluation will be determined by the investigator into 4 categories.

- Improved (Symptoms of ulcerative colitis have improved or showed adequate maintenance effect after taking Xeljanz®)
- Unchanged (Symptoms have not changed much since taking Xeljanz®)
- Aggravated (Symptoms have worsened after taking Xeljanz®)
- Not assessable

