### **5.2. Handling of Missing and Incomplete Data**

#### **5.2.1. Handling of Missing Data**

If data are missing or if a subject decided to discontinue from the study, there will be no imputation applied except as specified in section 5.2.2. The impact of missing data will be evaluated as appropriate.

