## **Statistical Analysis Plan for rPMS**

presented in frequency and percentage.

- Achieved
- Not achieved

4) Clinical response

- Clinical response at week 8 ( $\pm 15$  days), week 16 ( $\pm 15$  days), week 24 ( $\pm 15$  days) will be presented in frequency and percentage.
- Achieved
- Not achieved

5) Final efficacy assessment by the investigator

- Final efficacy assessment by the investigator classified as follows will be presented in frequency and percentage.

[Effective]

- Improved

[Not-effective]

- Unchanged

- Aggravated

6) Effective rate by demographic and other baseline characteristics

- Effective rate and 95% C.I will be presented by categorical variables of demographic and other baseline characteristics.
- To identify statistically significant difference in the effective rate by categorical variables of demographic and other baseline characteristics, Chi-square test ( $\chi^2$  test) or Fisher's exact test (if the expected frequency for each cell under 5 is more than 20%) will be performed.

7) Analysis of factors that affect the efficacy

- In the re-examination report, logistic regression of multivariate analysis will be performed and an odds ratio with 95% C.I and p-value will be presented to identify the factors that affect effective rate in demographic and other baseline characteristics.

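### The week-24 remission, response and healing tables have no last-assessment row and no stated denominator, so their rates probably favour patients who stayed on drug

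*SAP*

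**What the plan says.** **Who is analysed.** Protocol 7.7.2 includes early stoppers in the effectiveness analysis "based on the last assessment performed at the time of treatment discontinuation if the patient does not complete the 24 weeks of treatment". SAP 3.2 repeats this for the efficacy set ("or based on the last assessment performed at the time of treatment discontinuation if the patient does not complete the 24 weeks of treatment"), then excludes "Subjects who are have been administrated Xeljanz® for less than 8 weeks (56 days").

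**What is collected.** Protocol 7.2.5 has data collected "from the time of initiating administration of Xeljanz until 24 weeks of treatment (52 weeks of treatment for the long-term users"). For non-completers, SAP 4.2 says "relevant data should be collected based on the last assessment performed at the time of treatment discontinuation". No visit is mandatory.

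**What is tabulated (SAP 6.3).**
- Item 1, Mayo scores: values at weeks 8, 16 and 24, plus change from baseline to the last value, with a test.
- Items 2–4, healing, remission and response: by-week rows only. For healing: "Mucosal healing at week 8 ( $\pm 15$ days), week 16 ( $\pm 15$ days), week 24 ( $\pm 15$ days) will be presented in frequency and percentage". Item 4 has the same structure: "Clinical response at week 8 ( $\pm 15$ days), week 16 ( $\pm 15$ days), week 24 ( $\pm 15$ days) will be" shown as counts and percentages. The outcomes are Achieved and Not achieved.
- Items 5–7, the investigator's final rating: not tied to a week.

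**Missing data.** SAP 5.2.1 applies one rule to gaps in the data and to dropout alike: "if a subject decided to discontinue from the study, there will be no imputation applied except as specified in section 5.2.2". Section 5.2.2 deals only with disease duration and the treatment end date.

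The SAP does not say whether the percentages in items 2–4 are of the efficacy set or of patients assessed in the window.

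**The concern.** The SAP admits early stoppers on a particular assessment, uses such a last value in item 1, and then gives it no row in the three tables that report the disease-specific binary outcomes. The same patient can count in the last-value test and in the investigator's effective rate, yet be absent from week-24 remission.

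This matters because stopping is related to outcome. The reasons the CRF offers (Protocol 7.2.5.1) are adverse event, lack of effectiveness, and others. If patients who fail leave the later rows, the percentages can rise from week 8 to week 24 with no patient improving. The 56-day rule has already removed the earliest stoppers, so this would be a second layer of selection.

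**Working it through.** The documents give no expected rate, dropout figure or power statement for these outcomes, so there is no planned figure to reproduce.

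**1. Windows.** Week w covers days 7w − 15 to 7w + 15.
- Week 8: 56 ± 15 = days 41–71
- Week 16: 112 ± 15 = days 97–127
- Week 24: 168 ± 15 = days 153–183

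**2. Where a discontinuation assessment falls.** A patient in the efficacy set who stops short of 24 weeks stops on one of days 56–167, which is 112 possible days. Assume the assessment is made on the stop day.

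| Stop day | Number of days | Share of 112 | Window |
|---|---|---|---|
| 56–71 | 16 | 14% | week 8 |
| 72–96 and 128–152 | 25 + 25 = 50 | 45% | none |
| 97–127 | 31 | 28% | week 16 |
| 153–167 | 15 | 13% | week 24 |

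The assessment misses the week-24 row on 112 − 15 = 97 days (87%). It misses both the week-16 and week-24 rows on 50 + 16 = 66 days (59%). These are shares of calendar days, not of patients; the distribution of stop days is unknown.

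**3. Example.** A patient who stops at 14 weeks (day 98) falls in the week-16 window and can be counted there. That patient has nothing for week 24. A patient who stops on day 140 has a discontinuation assessment that enters none of the three tables.

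**4. Effect on the week-24 rate.** Let r be the rate among patients assessed at week 24, d the share of the efficacy set that stopped with no week-24 assessment, and q the rate at their discontinuation assessment. Everyone else is taken as assessed. All three are assumptions.
- Observed cases: r
- Stoppers counted on their last assessment: (1 − d)r + dq
- Stoppers counted as Not achieved: (1 − d)r

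| r | d | Observed | q = 0 | q = 10% |
|---|---|---|---|---|
| 50% | 20% | 50% | 40% | 42% |
| 50% | 30% | 50% | 35% | 38% |
| 50% | 40% | 50% | 30% | 34% |
| 30% | 20% | 30% | 24% | 26% |
| 30% | 30% | 30% | 21% | 24% |
| 30% | 40% | 30% | 18% | 22% |

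The gap is d(r − q): 8–20 points at r = 50% and 4–12 points at r = 30%. It does not depend on the number enrolled.

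**5. The unstated denominator.** If percentages are of the whole efficacy set, the printed rate is (1 − d)r, the q = 0 column. From the same data the two readings differ by dr, which is 10–20 points at r = 50%. Even on the whole-set reading, a stopper who had achieved the outcome is lost unless assessed inside the window: dq = 2–4 points at q = 10%.

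**The case against.** Several points on the other side stand.

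- **Some discontinuation assessments do count.** A reader might infer that they have no place at all in items 2–4, or that the week-16 and week-24 rates describe only patients still on drug. The SAP does not support that: nothing bars an assessment from the window it falls in, so stops on days 97–127 can count at week 16 and stops on days 153–167 at week 24.
- **The denominator is open.** Section 6.3 refers only to the efficacy set, and the dummy tables are not visible. If the whole set is the denominator, patients without a score already lower the rate. That fits poorly with a no-imputation rule, and with mucosal healing reported only where endoscopy was done, but it is not excluded.
- **No direct contradiction of the protocol.** A reader might infer that Protocol 7.7.2 requires the last assessment in every table. It defines who is analysed and on what data; Protocol 7.1 and 7.3.2 name weeks 8, 16 and 24 for these outcomes, and the SAP follows them.
- **Stoppers appear elsewhere.** Item 1 and items 5–7 include them, and SAP 6.1.6 tabulates reasons for stopping. Items 2–4 are secondary, single-arm and descriptive.
- **SAP 5.2.1 also promises to assess the effect of missing data where appropriate.** It names no method, so it does not close the gap.
- **Not every missing score is a failure.** Some patients stop for other reasons, and with no mandatory visits some still on drug will miss a window. The direction of bias from those is unknown.

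**Conclusion.** Items 2–4 lack a rule for discontinuation assessments outside the windows, and lack a denominator. On the most natural reading, observed cases, the week-24 rates favour patients who stayed on drug; week 16 is affected less. A plausible size is 8–20 percentage points at 50% observed remission with 20–40% stopped. This rests on assumed inputs, on all remaining patients being assessed, and on remission in stoppers of 0–10%. The upper end needs no stopper to be in remission.

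A bias of 10–20 points should not be read as demonstrated: the documents supply neither the dropout nor the remission rate, and the direction depends on the denominator. What they do show is that two analysts could print different headline rates from the same data, and that item 1 and items 2–4 treat the same patients differently. The outcomes are secondary, so this should be corrected but does not undermine the primary safety objective.

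**What to change.** In SAP 6.3 items 2–4:

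1. Add a row *week 24 or last assessment at discontinuation*. For mucosal healing, restrict it to patients with an endoscopy at or before discontinuation.
2. State the denominator of every percentage.
3. Show n assessed against n in the efficacy set for each window.
4. Keep the by-week rows, which the protocol specifies, and label them as observed cases.
5. For remission and clinical response, add a sensitivity analysis that counts every efficacy-set patient without a usable score as Not achieved, whatever the reason for stopping and including patients still on drug but not seen. Write this as an explicit exception to SAP 5.2.1.

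The non-responder analysis belongs in a sensitivity role: missing scores in patients who stopped for other reasons, or who were simply not seen, are not clearly failures.

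The cost is SAP wording and one or two extra rows per table. No new data are needed, since the plan already calls for the discontinuation assessment. The reported rates will probably be less favourable.

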## **Statistical Analysis Plan for rPMS**

presented in frequency and percentage.

- Achieved
- Not achieved

4) Clinical response

- Clinical response at week 8 ( $\pm 15$  days), week 16 ( $\pm 15$  days), week 24 ( $\pm 15$  days) will be presented in frequency and percentage.
- Achieved
- Not achieved

5) Final efficacy assessment by the investigator

- Final efficacy assessment by the investigator classified as follows will be presented in frequency and percentage.

[Effective]

- Improved

[Not-effective]

- Unchanged

- Aggravated

6) Effective rate by demographic and other baseline characteristics

- Effective rate and 95% C.I will be presented by categorical variables of demographic and other baseline characteristics.
- To identify statistically significant difference in the effective rate by categorical variables of demographic and other baseline characteristics, Chi-square test ( $\chi^2$  test) or Fisher's exact test (if the expected frequency for each cell under 5 is more than 20%) will be performed.

7) Analysis of factors that affect the efficacy

- In the re-examination report, logistic regression of multivariate analysis will be performed and an odds ratio with 95% C.I and p-value will be presented to identify the factors that affect effective rate in demographic and other baseline characteristics.

